1.1 Background

Axial spondyloarthritis (axSpA) is a type of spondyloarthritis mainly affecting the axial skeleton, characterized by spinal inflammation and inflammatory back pain. AxSpA is among the most common chronic inflammatory joint disorders, with recent estimates of prevalence in Caucasian populations in the range of 1–2% ([Baraliakos and Braun 2011](#)). Patients with chronic back pain (onset before 45 years of age) are classified as having axSpA if they fulfill either the clinical arm or the imaging arm of the Assessment of SpondyloArthritis International Society (ASAS) classification criteria ([Rudwaleit et al 2009](#)).

Based on the presence or absence of sacroiliitis on conventional X-ray radiographs, axSpA patients are further classified into two conditions: non-radiographic-axSpA (nr-axSpA) and ankylosing spondylitis (AS). Patients with evidence of sacroiliitis on X-ray fulfilling the 1984 modified New York diagnostic criteria ([van der Linden et al 1984](#)) are classified as having AS, whereas patients who do not show sacroiliitis on X-ray, but may show evidence of sacroiliitis on MRI, are classified as having nr-axSpA.

AS is characterized mainly by involvement of the axial skeleton and sacroiliac (SI) joints, but peripheral joints, entheses and extra-articular organs may also be affected. A significant proportion of AS patients may present with associated extra-articular manifestations such as uveitis, psoriasis, inflammatory bowel disease (IBD), or cardiovascular and pulmonary abnormalities. Generalized osteoporosis, as well as regional osteopenia are common in AS patients and predispose them to non-traumatic fractures, despite a predominantly younger age and male gender distribution. The presence of the Human Leukocyte Antigen (HLA)-B27 is strongly associated with AS; 90–95% of patients with AS who have European ancestry carry this marker. AS affects up to 1.1% of the population, is associated with significant morbidity and disability, and thus constitutes a major socioeconomic burden.

Studies and registry data have shown that nr-axSpA patients have similar levels of disease activity, pain, and health-related quality of life impairment as observed in AS patients ([Wallis et al 2013](#)). Disease parameters and response rates to treatment with tumor necrosis factor (TNF) antagonists are similar in patients with AS and nr-axSpA, supporting the concept that axSpA is a disease with distinct stages ([Song et al 2013](#)). Furthermore, with a longer duration of symptoms, most patients who start with nr-axSpA ultimately develop radiographic evidence consistent with AS. In an investigation of 329 patients with axSpA, evidence of radiographic sacroiliitis was present in 40–86% of patients, in accordance with the duration of symptoms (<10 to > 20 years) ([Said-Nahal et al 2000](#)), with many nr-axSpA patients progressing to AS over time. Nonetheless, it is estimated that 10–15% of nr-axSpA patients do not develop radiographic sacroiliitis ([Sieper and van der Heijde 2013](#)). Thus, nr-axSpA may represent an early stage of AS, but may also be a form of the disease which causes much pain without leading to structural changes of the axial skeleton ([Baraliakos and Braun 2015](#)). In short, patients recognized as having axSpA, either with AS or nr-axSpA, present with similar clinical characteristics, the same burden of disease, and the same response to anti-inflammatory medication. A study evaluating the efficacy and safety of secukinumab 150 mg s.c. q4w vs. placebo (CAIN475H2315) in patients with nr-axSpA is currently ongoing.

First-line medication of mild AS consists of non-steroidal anti-inflammatory drugs (NSAIDs). Treatment of NSAID-refractory AS is hampered by the lack of efficacy of virtually all conventional disease modifying anti-rheumatic drugs (DMARDs), including methotrexate (MTX). As an exception, peripheral arthritis associated with AS may respond to sulfasalazine and methotrexate. TNF blocking agents were successfully added to the armamentarium to treat AS (Braun et al 2002) and subsequently demonstrated prolonged efficacy up to eight years of follow-up (Baraliakos et al 2011). However, upon discontinuation of TNF blockers the disease relapses quickly (Baraliakos et al 2005), indicating that the inflammatory process may have only been inhibited but not completely abolished.

Secukinumab is a fully human IgG1 antibody that selectively binds to and neutralizes the proinflammatory cytokine interleukin-17A (IL-17A). Secukinumab targets IL-17A, inhibiting its interaction with the IL-17 receptor expressed on various cell types including keratinocytes and synoviocytes. As a result, secukinumab inhibits the release of proinflammatory cytokines, chemokines and mediators of tissue damage and reduces IL-17A-mediated contributions to autoimmune and inflammatory diseases, including psoriasis, psoriatic arthritis (PsA) and AS.

To date, s.c. secukinumab is approved in over 90 countries for the clinical management of PsA and AS.

1.2 Purpose

The purpose of this global study is to demonstrate the efficacy, safety, and tolerability of an intravenous (i.v.) regimen of secukinumab compared to placebo in subjects with active axSpA, including AS and nr-axSpA at Week 16 despite current or previous NSAID, conventional DMARD and/or anti TNF therapy. In addition, to further support efficacy and safety of an i.v. regimen, data will be collected for up to 52 weeks of treatment. Efficacy and safety data may be used to support the registration of i.v. secukinumab in the US and other countries for treatment of subjects with active axSpA.

[figure not shown]
2 Objectives and endpoints

Table 2-1 Objectives and related endpoints

Objective(s)	Endpoint(s)
Primary objective(s)	Endpoint(s) for primary objective(s)

 To demonstrate that the efficacy of i.v. secukinumab at Week 16 is superior to placebo in subjects with active axSpA (AS and nr-axSpA) based on the proportion of subjects achieving an ASAS40 (Assessment of SpondyloArthritis International Society criteria) response. 	
 ASAS40 response at Week 16, defined as improvement of $\geq 40\%$ and an absolute improvement from baseline of ≥ 20 units (range 0–100) in ≥ 3 of the following 4 domains: back pain [10 cm visual analogue scale (VAS)], patient global assessment of disease activity (10 cm VAS), physical function (BASFI; range 0–100) and inflammation (mean score

[figure not shown]
Objective(s)	Endpoint(s)
	of items 5 and 6 of the BASDAI; both 10 cm VAS) without any worsening in the remaining domain.
Secondary objective(s)	Endpoint(s) for secondary objective(s)

 • To demonstrate that the efficacy of i.v. secukinumab at Week 16 is superior to placebo based on the proportion of subjects achieving Ankylosing Spondylitis Disease Activity Score (ASDAS)-C-Reactive Protein (CRP) major improvement • To demonstrate that the efficacy of i.v. secukinumab at Week 16 is superior to placebo based on the change from baseline in total Bath Ankylosing Spondylitis Disease Activity Index (BASDAI) • To demonstrate that the efficacy of i.v. secukinumab at Week 16 is superior to placebo based on the proportion of subjects meeting the ASAS 5/6 response criteria • To demonstrate that the efficacy of i.v. secukinumab at Week 16 is superior to placebo based on Bath Ankylosing Spondylitis Functional Index (BASFI) • To evaluate the efficacy of i.v. secukinumab compared to placebo after 16 weeks of treatment by assessing Short Form-36 Physical Component Summary (SF-36 PCS) • To demonstrate that the efficacy of i.v. secukinumab at Week 16 is superior to placebo based on the change from baseline in Ankylosing Spondylitis Quality of Life (ASQoL) scores • To demonstrate that the efficacy of i.v. secukinumab at Week 16 is superior to placebo based on the change from baseline in high sensitivity C-Reactive Protein (hsCRP) • To demonstrate that the efficacy of i.v. secukinumab at Week 16 is superior to placebo based on the proportion of subjects achieving an ASAS20 response 	
 • ASDAS-CRP major improvement defined as a change (decrease) in the score of at least 2.0 units • Change from baseline in total BASDAI • Subjects achieving ASAS 5/6 response defined as: improvement of $\geq 20\%$ in at least five of six domains • Change from baseline of BASFI • Absolute & percent change from baseline in SF-36 PCS • Absolute & percent change from baseline in ASQoL • Change from baseline in hsCRP • The ASAS Response Criteria (ASAS20) is defined as an improvement of $\geq 20\%$ and ≥ 1 unit on a scale of 10 in at least three of the four main domains and no worsening of $\geq 20\%$ and

[figure not shown]
Objective(s)	Endpoint(s)

• To demonstrate that the efficacy of i.v. secukinumab at Week 16 is superior to placebo based on the proportion of subjects achieving Ankylosing Spondylitis Disease Activity Score (ASDAS)-C-Reactive Protein (CRP) inactive disease• To demonstrate that the efficacy of i.v. secukinumab at Week 16 is superior to placebo based on the proportion of subjects achieving ASAS partial remission• To demonstrate that the efficacy of i.v. secukinumab at Week 16 is superior to placebo based on the change from baseline in Pittsburgh Sleep Quality Index (PSQI)• Overall safety and tolerability of i.v. secukinumab compared to placebo as assessed by physical exams, vital signs, laboratory assessments and adverse event monitoring	
• ≥ 1 unit on a scale of 10 in the remaining domain.• ASDAS-CRP inactive disease as defined by an ASDAS-CRP score below 1.3• ASAS partial remission criteria are defined as a value not above 2 units in each of the four main ASAS domains on a scale of 0-10• Change from baseline in PSQI• Physical exams, vital signs, laboratory assessments, and adverse event monitoring

Objective(s)

Endpoint(s)

Objective(s)	Endpoint(s)

3 Study design

This multicenter study uses a randomized, double-blind, placebo-controlled, parallel-group design to study the efficacy, safety, and tolerability of treatment with intravenous secukinumab (initial dose of 6 mg/kg followed thereafter with 3 mg/kg administered every four weeks starting at Week 4) in subjects with active axSpA. The study population consists of approximately 400 subjects with active AS and approximately 100 subjects with active nr-axSpA, despite current or previous NSAID, conventional DMARD and / or TNF inhibitor therapy, or intolerance to these therapies. A screening (SCR) period of up to 10 weeks will be used to assess eligibility, followed by randomization to 52 weeks of study treatment.

At baseline, subjects with active AS and nr-axSpA will be randomized to one of the two treatment groups:

- Group 1: approximately 200 AS subjects and approximately 50 nr-axSpA subjects; These subjects will receive secukinumab 6 mg/kg i.v. at randomization (Baseline (BSL) visit), followed by the administration of secukinumab 3 mg/kg i.v. every four weeks starting at Week 4 through Week 48 (exposure through Week 52).
- Group 2: approximately 200 AS subjects and approximately 50 nr-axSpA subjects; These subjects will receive i.v. placebo at randomization (BSL visit), Weeks 4, 8, and 12 ,

followed by the administration of secukinumab 3 mg/kg i.v. at Week 16 and every four weeks through Week 48 (exposure through Week 52).

[figure not shown]
This study will consist of 4 periods totaling 70 weeks: the screening period (up to 10 weeks), the treatment period 1 (total duration of 16 weeks) and the treatment period 2 (total duration of 36 weeks) followed by the safety follow up period of 8 weeks after the end of treatment visit (i.e., Week 52).

The subjects will be stratified at randomization according to disease condition (i.e., AS or nr-axSpA). No more than 20% TNF Inhibitor Incomplete Responders (TNF-IR) subjects will be enrolled in the study. Starting at Week 16, all subjects will switch to open-label intravenous secukinumab, including all placebo subjects.

No subject will be on placebo treatment after Week 16, because axSpA is considered a chronic disease with no 'true' and lasting placebo response. However, all subjects and investigators/site staff will remain blinded to the original randomized treatment group assignment (secukinumab treatment vs placebo). Study treatment will continue up to Week 52. An end of treatment visit (i.e., Week 52) is to be done 4 weeks after last study treatment administration and a post treatment follow-up visit (i.e., Week 60) is to be done 8 weeks after the end of treatment visit for all subjects (regardless of whether they complete the entire study as planned or discontinue prematurely). All i.v. infusions will be performed at the study site and site personnel will administer the infusions to subjects.

Rescue medication is not allowed until Week 16. However, subjects who are deemed by the investigator not to be benefiting from the study treatment based on safety and efficacy assessments or for any reason of their own accord will be free to discontinue participation in the study at any time. The study will have a primary endpoint analysis at Week 16. Therefore, the primary analysis will be performed with Week-16 data once the last subject has completed the Treatment Period 1.

Figure 3-1 Study Design

4 Rationale

4.1 Rationale for study design

The double-blind, randomized, parallel-group, placebo-controlled design used in this study is aligned with Phase III trials of other biologics and is in accordance with EMA (European Medical Agency) guidelines (EMA 2017) and available precedent. The treatment duration of the placebo group has been kept short and the group will be re-assigned to active treatment once the Week 16 visit for primary endpoint assessments has been reached. Although study treatment is open label secukinumab i.v. starting at Week 16, blinding to original treatment assignment will be maintained, so as to ensure unbiased efficacy and safety assessments for the remainder of the study.

[figure not shown]
A non-dosing visit has been included at Week 25. Efficacy measures and a PK sample collected at that visit will be used to assess the dynamic of the efficacy response in steady or quasi-steady state condition between the administration of two doses as well as its relationship with secukinumab concentration. This will allow exploration of the possible effect of the route of administration on the efficacy response.

4.1.1 Rationale for choice of background therapy

Clinical management of axSpA by pharmacotherapy includes the use of NSAIDs and conventional DMARDs, and if insufficient response, biologic agents (i.e., TNF-inhibitor therapy or anti-IL17 agents).

This study intends to enroll patients with active disease despite current or previous NSAIDs, conventional DMARDs and/or TNF inhibitor therapy or intolerance to these therapies. A background of NSAID therapy and/or concomitant therapy with methotrexate (≤ 25 mg/week) or sulfasalazine (≤ 3 g/day) will be acceptable, if dose and route of administration have been stable for at least two weeks with NSAIDs and/or four weeks with MTX or sulfasalazine, prior to the randomization visit. Inclusion of patients with active axSpA who are TNF-IR (up to 20% in each group) in the study also makes the background patient population more representative of the real world clinical scenario.

4.2 Rationale for dose/regimen and duration of treatment

Hence, the proposed i.v. regimen is expected to deliver an exposure within the approved s.c. doses of secukinumab. Considering the large amount of clinical data collected so far and understanding of the PK profile for secukinumab in AS, it is expected that the clinical response with the proposed i.v. regimen will be similar to that observed with current approved s.c. regimens.

4.3 Rationale for choice of control drugs (comparator/placebo) or combination drugs

A placebo arm up to the primary endpoint at Week 16 is included in this study. Due to the nature of the disease and the outcome measures used (ASAS criteria), a placebo arm is necessary to reliably evaluate the efficacy and safety of the active drug. The continuation of the placebo

group up to the primary endpoint assessment at Week 16 can be supported from an ethical standpoint, as subjects can continue on a range of concomitant treatments.

The parallel-group placebo controlled design used in this study is aligned with Phase III trials of other biologics in this disease area including registration studies of s.c. secukinumab in axSpA and is also in accordance with EMA guidelines (EMA 2017). The treatment duration of the placebo group is relatively short and the placebo group will be re-assigned to active treatment at Week 16. The regular assessment of disease activity ensures that subjects who are experiencing worsening of disease in any of the treatment groups can exit the study at any time upon their own accord or based on the advice of the investigator.

4.4 Purpose and timing of interim analyses/design adaptations

The primary endpoint analysis (Week-16 analysis) will be performed after all subjects complete the Week-16 visit in order to support regulatory filings.

Additional analyses may be performed to support health authority interactions, as necessary.

The investigators, site personnel, subjects and monitors will remain blinded to the original treatment assignment groups until Week-60 analysis has been completed.

4.5 Risks and benefits

Secukinumab has demonstrated either preliminary or confirmed efficacy in several inflammatory diseases including psoriasis, psoriatic arthritis and ankylosing spondylitis. The safety profile of secukinumab is primarily based on the aggregate safety data from 10 large completed phase II/III psoriasis trials. The evaluation of safety data from completed phase II/III AS trials did not show additional safety concerns.

Secukinumab was generally safe and well-tolerated. The most frequently reported adverse events are infections, especially upper respiratory tract with secukinumab relative to placebo.

There was an increase in mucosal or cutaneous candidiasis with secukinumab compared to placebo, but the cases were mostly mild or moderate in severity, non-serious, and responsive to standard treatment.

There was a small increase in mild neutropenia cases with secukinumab compared to placebo.

Common Toxicity Criteria (CTC) AE grade 3 neutropenia ($<1.0-0.5 \times 10^9/L$) was uncommonly observed with secukinumab, most were transient and reversible without a temporal relationship to serious infections.

Hypersensitivity reactions including urticarial and a rare event of anaphylactic reaction to secukinumab were also observed in clinical studies.

Taking into account the individual risks as outlined above, the expected risk profile of the i.v. regimen of secukinumab from a mechanism of action perspective is anticipated to be similar to that seen with the approved s.c. secukinumab regimens. The risk to subjects in this trial will be minimized by compliance with the eligibility criteria, close clinical monitoring and extensive guidance to the investigators, provided in the current version of the Investigator's Brochure (IB).

Women of child bearing potential must be informed that taking the study treatment may involve unknown risks to the fetus if pregnancy were to occur during the study and must agree that in order to participate in the study they must adhere to the contraception requirements outlined in the exclusion criteria. If there is any question that the subject will not reliably comply, they should not be entered or continue in the study.

From the standpoint of the overall risk-benefit assessment, the current trial with secukinumab is justified.

5 Population

The study population will consist of male and female subjects (≥ 18 years old at the time of consent) with active axSpA (AS or nr-axSpA). The diagnosis of axSpA must fulfill the ASAS criteria of inflammatory back pain for at least 6 months AND onset before 45 years of age. For a diagnosis of AS, subjects must fulfill the Modified New York criteria for AS (see [Section 16.2](#)) with prior documented radiological evidence (x-ray or a radiologists report).

Subjects with nr-axSpA (no definitive radiographic evidence of changes in the sacroiliac joints that would meet the modified New York criteria for AS) must fulfill the following ASAS classification criteria for axSpA:

- a. Sacroiliitis on MRI (centrally read) with ≥ 1 SpA feature OR HLA-B27 is positive with ≥ 2 SpA features AND
- b. Objective signs of inflammation at screening, evident by either MRI with SI joint inflammation (centrally read) AND / OR hsCRP $>$ ULN (as defined by the central lab)

In addition, all subjects must have evidence of active axSpA as measured by the following three assessments:

- total BASDAI ≥ 4 cm on a scale of 0-10 cm
- spinal pain as measured by BASDAI question #2 ≥ 4 cm (0-10 cm)
- total back pain as measured by visual analog scale (VAS) ≥ 40 mm (0-100 mm)

Included subjects must have evidence of active disease despite current or previous NSAID, conventional DMARD and/or anti-TNF therapy.

This is a global interventional study and it is expected that approximately 500 subjects are randomized (approximately 400 subjects with active AS and approximately 100 subjects with nr-axSpA) to evaluate the efficacy and safety of i.v. secukinumab in this subject population.

A screening failure rate of 25% and post-randomization drop-out rate of 10% prior to the time of the primary endpoint assessments (Week 16) are anticipated. Enrollment will stop as soon as the target number of randomized subjects is reached.

No more than 20% TNF-IR subjects will be enrolled in the study.

Subjects can be re-screened only once and no study-related re-screening procedure should be performed prior to written re-consent by the subject. Mis-randomization occurs when a subject who does not meet all eligibility criteria receives a randomization number in IRT in error; mis-randomized subjects will be treated as screen failures and will not be re-screened. However, if the subject randomized in error was dosed then he/she will be discontinued.

5.1 Inclusion criteria

Subjects eligible for inclusion in this study must meet **all** of the following criteria:

1. Subject must be able to understand and communicate with the investigator, comply with the requirements of the study, and must give written, signed and dated informed consent before any study assessment is performed
2. Male and non-pregnant, non-lactating female patients ≥ 18 years of age
3. Diagnosis of axSpA according to ASAS criteria
 - a. Inflammatory back pain for at least 6 months
 - b. Onset before 45 years of age
4. For subjects with AS: Diagnosis of AS with prior documented radiologic evidence (x-ray or radiologist's report) fulfilling the Modified New York criteria for AS
5. For subjects with nr-axSpA:

X-ray of SIJ negative (centrally read) for AS by Modified NY criteria AND

 - a. Sacroiliitis on MRI (centrally read) with ≥ 1 SpA feature OR HLA-B-27 positive with ≥ 2 SpA features AND
 - b. Objective signs of inflammation at screening, evident by either MRI with SIJ inflammation (centrally read) AND / OR hsCRP > ULN (as defined by the central lab)
6. Active axial SpA assessed by BASDAI ≥ 4 cm (0-10 cm) at Baseline
7. Spinal pain as measured by BASDAI question #2 ≥ 4 cm (0-10 cm) at Baseline
8. Total back pain as measured by VAS ≥ 40 mm (0-100 mm) at Baseline
9. Subjects should have had inadequate response or failure to respond to at least 2 NSAIDs at an approved dose for a minimum of 4 weeks in total and a minimum of 2 weeks for each NSAID prior to randomization, or less than 4 weeks if therapy had to be withdrawn due to intolerance, toxicity or contraindications
10. Subjects who are regularly taking NSAIDs (including COX-1 or COX-2 inhibitors) as part of their AS or nr-axSpA therapy are required to be on a stable dose for at least 2 weeks before randomization
11. Subjects who are intolerant or have been inadequate responders to a TNF inhibitor (not more than one) will be allowed to enter into the study (not more than 20% per group). They must have experienced an inadequate response to previous or current treatment at an approved dose for at least 3 months prior to randomization, or have been intolerant to at least one administration of an anti-TNF agent. These subjects will undergo an appropriate wash-out period prior to randomization, if required
 - a. 4 weeks for Enbrel[®] (etanercept) – with a terminal half-life of 102 ± 30 hours
 - b. 8 weeks for Remicade[®] (infliximab) – with a terminal half-life of 8.0-9.5 days
 - c. 10 weeks for Humira[®] (adalimumab) – with a terminal half-life of 10-20 days (average 2 weeks)
 - d. 10 weeks for Simponi[®] (golimumab) – with a terminal half-life of 11-14 days
 - e. 10 weeks for Cimzia[®] (certolizumab) – with a terminal half-life of 14 days

12. Subjects taking methotrexate (MTX) (≤ 25 mg/week) or sulfasalazine (≤ 3 g/day) are allowed to continue their medication and must have taken it for at least 3 months and have to be on a stable dose for at least 4 weeks prior to randomization. Subjects on MTX must be on folic acid supplementation before randomization
13. Subjects who are on a conventional DMARD other than MTX or sulfasalazine must discontinue the DMARD 4 weeks prior to randomization, except for leflunomide, which must be discontinued 8 weeks prior to randomization, unless a cholestyramine washout has been performed
14. Subjects taking systemic corticosteroids must be on a stable dose of ≤ 10 mg/day prednisone or equivalent for at least 2 weeks before randomization

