6.3.2 Treatment assignment, randomization

At BSL visit, all eligible subjects will be randomized via Interactive Response Technology (IRT) to one of the treatment arms. The investigator or his/her delegate will contact the IRT after confirming that the subject fulfills all the inclusion/exclusion criteria. The IRT will assign a randomization number to the subject, which will be used to link the subject to a treatment arm and will specify a unique medication number for the first package of study treatment to be dispensed to the subject. The randomization number will not be communicated to any of the site staff.

Starting at Week 16, subjects who have been randomized to placebo at baseline will receive secukinumab 3 mg/kg i.v. up to Week 48. Although the investigator, site personnel and subjects are unblinded to current treatment assignment after Week 16 (as all subjects will be on secukinumab 3 mg/kg i.v starting at Week 16), original treatment assignment, as per baseline randomization, will remain blinded to the subject, investigator, and site personnel until after final database lock and analyses.

All efficacy and safety assessments should be done prior to calling IRT.

The randomization numbers will be generated using the following procedure to ensure that treatment assignment is unbiased and concealed from subjects and investigator staff. A subject randomization list will be produced by the IRT provider using a validated system that automates the random assignment of subject numbers to randomization numbers. These randomization numbers are linked to the different treatment arms, which in turn are linked to medication

numbers. A separate medication list will be produced by or under the responsibility of Novartis Global Clinical Supply (GCS) using a validated system that automates the random assignment of medication numbers to packs containing the study treatment.

The subjects will be stratified at randomization according to disease condition (i.e. AS or nr-axSpA). Not more than 20% of randomized subjects will be TNF-IR to ensure a representative subject population for the assessment of efficacy and safety.

The randomization scheme for subjects will be reviewed and approved by a member of the Randomization Office.

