12.4.2 Statistical model, hypothesis, and method of analysis

The estimand for primary endpoint is defined as follows:

- A. Population: defined through appropriate inclusion/exclusion criteria to reflect the targeted axSpA population (AS and nr-axSpA)
- B. Variable: composite of remaining on the study and on randomized treatment through 16 weeks and achieving ASAS40 response at 16 weeks
- C. Intercurrent event: the intercurrent event is captured through the variable definition
- D. Population-level summary: difference in proportions of responders between the secukinumab and placebo arms

The statistical hypothesis for ASAS40 being tested is that there is no difference in the proportion of subjects fulfilling the ASAS40 criteria at Week 16 in the secukinumab i.v. regimen versus placebo regimen.

Let p_0 denote the proportion of ASAS40 responders at Week 16 for placebo regimen and p_1 denote the proportion of ASAS40 responders at Week 16 for secukinumab i.v. regimen.

In statistical terms, $H_1: p_1 = p_0$, $H_{A1}: p_1 \neq p_0$, i.e.,

H_1 : secukinumab i.v. regimen is not different to placebo regimen with respect to ASAS40 response at Week 16

The primary analysis will be conducted via logistic regression with treatment and stratification factor (disease condition) as factors and weight as a covariate. Difference in marginal response proportions with p-value and 95% confidence interval (CI) will be presented comparing secukinumab i.v. regimen to placebo.

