12.8 Sample size calculation

12.8.1 Primary endpoint(s)

An overall type I error (2-sided) of 5% will be used to control type I error. Secukinumab i.v. regimen will be tested versus placebo with respect to the primary endpoint (ASAS40 response at Week 16). A sample size of 250 axSpA patients (200 AS patients and 50 nr-axSpA patients) per group is deemed appropriate to achieve adequate power for the primary and secondary endpoints for this study.

An ASAS40 response rate of about 28.2% for the AS population in the placebo group at week 16 was reported in a published phase III study (CAIN457F2320). The ASAS40 response to secukinumab 150 mg is estimated to be 44.9% in the AS population based on the lower bound of the 90% confidence interval of risk difference from the meta-analysis of 3 phase III studies (CAIN457F2310, CAIN457F2320 and CAIN457F2308). With 250 patients per treatment group (200 AS patients and 50 nr-axSpA patients), there would be approximately 96% power to detect a treatment difference of 16.7% in ASAS40 response rates between secukinumab and placebo in the evaluation of the primary efficacy hypothesis at Week 16 (Chi Square test, NQuery 7.0). The overall sample size will be 500 patients (400 AS patients and 100 nr-axSpA patients) for a randomization ratio of 1:1.

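### The 20% limit on TNF-IR subjects is stated per treatment group in some sections and trial-wide in others, and the described randomization does not guarantee the per-group version

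*Protocol*

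**What the plan says.** **Per-group wording.** Inclusion criterion 11, in Protocol Section 5.1 and in the Protocol summary, admits TNF-IR subjects but "not more than 20% per group". Section 4.1.1 describes the population as including patients who are "TNF-IR (up to 20% in each group"). Sections 3 and 6.1.3 use Group 1 and Group 2 for the treatment arms, so the natural reading of group is arm.

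**Trial-wide wording.** Section 6.3.2, which describes the randomization, states: "Not more than 20% of randomized subjects will be TNF-IR to ensure a representative subject population". Protocol Sections 3 and 5 and SAP Section 1.1 likewise apply the 20% to the study as a whole.

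**Allocation and model.** Disease condition (AS or nr-axSpA) is the only stratification factor. Section 12.4.2 reads: "The primary analysis will be conducted via logistic regression with treatment and stratification factor (disease condition) as factors and weight as a covariate". There is no TNF-IR term.

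**Related provisions.** Prior TNF inhibitor use (yes/no) is summarized at baseline (Protocol Section 12.2). Supportive logistic models with other baseline characteristics (Protocol Section 12.4.4) and an analysis by previous TNF inhibitor use (SAP Section 2.2.2) are both worded as optional.

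**The concern.** With 250 subjects per arm, the two wordings are different rules: at most 50 TNF-IR subjects in each arm, or at most 100 in the trial. The second does not imply the first. Meeting the first would need stratification on TNF-IR together with a suitable overall cap, or an arm-specific limit in the IRT. The documents describe neither.

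The stricter rule also sits inside an eligibility criterion. Section 6.3.2 has the investigator confirm all criteria before contacting the IRT, yet a blinded site cannot know the TNF-IR share of an arm. A trial run exactly as described could therefore breach its own inclusion criterion through chance alone.

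On the analysis side, a baseline characteristic that the sponsor chose to limit is missing from the primary model, and no analysis that would address an imbalance in it is firmly planned. What is at stake is consistency between the documents and a little precision.

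**Working it through.** **1. The plan's own figure.** Inputs from Protocol Section 12.8.1: "An overall type I error (2-sided) of 5% will be used to control type I error"; "An ASAS40 response rate of about 28.2% for the AS population in the placebo group at week 16"; "The ASAS40 response to secukinumab 150 mg is estimated to be 44.9% in the AS population"; 250 per arm.

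- Difference: 0.449 − 0.282 = 0.167. Mean rate: 0.3655.
- SE under the null: √(2 × 0.3655 × 0.6345 / 250) = 0.0431.
- SE under the alternative: √((0.449 × 0.551 + 0.282 × 0.718) / 250) = 0.0424.
- Power: Φ((0.167 − 1.96 × 0.0431) / 0.0424) = Φ(1.95) = 97.4%.

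With a continuity correction, power is 96.8%. With 225 per arm (the anticipated 10% drop-out removed), it is 95.9%. The stated "approximately 96% power to detect a treatment difference of 16.7% in ASAS40 response rates" is reproduced within two points.

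**2. Does a trial-wide cap hold each arm to 50?** Let K be the number of TNF-IR subjects among 500, and X the number in one arm of 250. Without stratification on TNF-IR, X is hypergeometric:

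P(X = x) = C(K, x) C(500 − K, 250 − x) / C(500, 250)

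The limit fails if X > 50 or K − X > 50. At K = 100, only an exact 50/50 split avoids this.

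| TNF-IR subjects enrolled (K) | Probability that one arm exceeds 50 |
|---|---|
| 100 | 91% |
| 95 | 49% |
| 90 | 20% |
| 85 | 5.6% |
| 80 | 1.0% |
| 70 | 0.01% |

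At K = 100, one arm has 55 or more with probability 31%.

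**3. Size of the imbalance at K = 100.** Var(X) = 250 × 0.2 × 0.8 × 250/499 = 20.04, so SD(X) = 4.48. The arm difference is 2X − K, with SD 8.95 subjects, or 8.95/250 = 3.6 points of TNF-IR share (95% range ±7.0 points). Stratifying by disease condition hardly changes this. With TNF-IR spread evenly over 400 AS and 100 nr-axSpA subjects, the variance is 32 × 200/399 + 8 × 50/99 = 16.04 + 4.04 = 20.08.

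**4. Effect on the ASAS40 difference.** The documents give no response gap between TNF-IR and other subjects, so gaps of 10 and 20 points, equal in both arms, are assumed. The shift is the imbalance times the gap.

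| Assumed gap | Shift for a 1-SD imbalance | 95% range of shift | Variance explained by TNF-IR |
|---|---|---|---|
| 10 points | 0.36 points | ±0.7 points | 0.01 × 0.16 / 0.2249 = 0.7% |
| 20 points | 0.72 points | ±1.4 points | 0.04 × 0.16 / 0.2249 = 2.8% |

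Here 0.16 = 0.2 × 0.8, and 0.2249 is the mean of the two arms' response variances, (0.2474 + 0.2025)/2. For scale, the planned effect is 16.7 points, with SE 4.24 and a 95% CI half-width of 8.3 points.

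**5. Simulation** (200,000 trials per setting, K = 100, gaps of 5 to 25 points). The unadjusted estimate is centred on the true difference, and its type I error is 4.96% to 5.08%. Stratifying the test by TNF-IR moves the SD of the estimate from 4.24 to 4.23 points (gap 10) or 4.18 (gap 20). Power moves from 97.4% to 97.5% or 97.7%.

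**6. Would stratification alone secure 50 per arm?** Block size is not stated. Assume central blocks of 4 within TNF-IR by disease strata. Each of the two TNF-IR strata can then end up to 2 subjects out of balance, so the arms can differ by 4. At K = 100 that permits 52/48. At K = 96 (19.2% of 500) the worst case is 50/46.

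**The case against.** A reader might infer that the per-group limit cannot be met, and that a TNF-IR imbalance biases the ASAS40 result. The documents support neither reading.

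- **Cannot be met.** The 91% needs exactly 100 TNF-IR subjects. No expected share is given, and at 80 or fewer the limit would hold about 99% of the time by chance. The limit is not guaranteed, which is a weaker statement.
- **Bias.** Under randomization the imbalance averages zero, and the planned standard error and confidence interval already include it. Type I error is kept and the stated power is not affected. On the assumed gaps, a 1-SD imbalance moves the estimate by at most about 0.17 of a standard error (0.72/4.24).
- **Sponsor's intent.** The stated reason for the cap is a representative population. The documents do not say that TNF-IR predicts ASAS40.
- **Partly covered.** Supportive models and a TNF subgroup are foreseen, though only as options. Parts of Protocol Section 12 are redacted, and the supplied SAP covers the final analysis, so Week 16 supportive detail may exist elsewhere.
- **Timing.** SAP Sections 2.5 and 2.14 show the Week 16 analysis as already done. Changing the primary model then would be a change after unblinding.

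All of this stands and limits the modelling part to a small gain. It does not remove the contradiction over the cap. Reading group as disease group would not help either: that would be a third rule, equally at odds with the trial-wide wording.

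A request to add baseline hsCRP to the model might also seem to follow. The documents do not support it: they do not say that hsCRP predicts ASAS40, and the ASDAS-CRP response models already adjust for a baseline score that contains CRP.

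**Conclusion.** The concern holds as an inconsistency between sections, with a minor point about precision. The per-group cap is a property that the described design does not guarantee. A breach is likely only if enrollment of TNF-IR subjects comes close to the trial-wide limit, and it is rare at 80 or fewer. These probabilities rest on 250 per arm and on allocation unrelated to TNF-IR status.

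The validity of the primary comparison is not in question. Omitting TNF-IR from the model costs roughly 0.7% to 2.8% of the variance, and that range rests on 20% prevalence and the assumed gaps of 10 to 20 points.

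**What to change.** 1. **Reconcile the cap.** State it as an overall 20% in inclusion criterion 11 (Protocol summary and Section 5.1) and in Section 4.1.1, to match Sections 3, 5 and 6.3.2 and the SAP. If a per-arm limit is really intended, add TNF-IR (yes/no) as an IRT stratification factor and set the overall cap slightly below 20%, for example 96 subjects under the assumed blocks of 4. This alternative is open only before randomization is under way.
2. **Use the recorded covariate.** Before unblinding, add TNF-IR status (yes/no) as a factor in the primary ASAS40 logistic model and keep the marginal risk difference as the estimate. If Week 16 data are already unblinded, leave the primary model unchanged, commit to a TNF-IR-adjusted model labelled as a sensitivity analysis, and report TNF-IR counts by arm.

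The cost is wording in three places and one model term or one added analysis. Prior TNF inhibitor use is already recorded, so no new data are needed.
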